3.1. Study Rationale

CCI

Study I6T-MC-AMAL (AMAL) is a Phase 1 study designed to determine whether the pharmacokinetics (PK) and tolerability of LY3074828 are affected following these changes to the investigational product, when administered subcutaneously to healthy subjects. The potential effect of administering the same volume as a single injection (1 × 2-mL) or as 2 injections (2 × 1-mL) on PK and tolerability will also be investigated during subcutaneous (SC) administration (see Section 5.4 for rationale for study design). In addition, the absolute bioavailability of LY3074828 Drug Product produced by the new process will be investigated by inclusion of an intravenous (IV) LY3074828 treatment.

3.2. Background

Interleukin-23 (IL-23), a member of the interleukin-12 (IL-12) family of cytokines, is a heterodimeric protein composed of 2 subunits: the p40 subunit, which IL-23 shares with IL-12, and the p19 subunit, which is believed to be specific to IL-23. Interleukin-23 is produced by antigen-presenting cells, such as dendritic cells and macrophages (Oppmann et al. 2000; Andersson et al. 2004). Interleukin-23 is critically involved in the maintenance and amplification of T helper 17 (Th17) cells. In addition to Th17 cells, many innate immune cells respond to IL-23 and are important both in resistance to infection and in mediating pathology in many autoimmune or inflammatory diseases including ulcerative colitis and Crohn's disease (CD) (Croxford et al. 2014).

Treatment of autoimmune or inflammatory diseases with IL-23-targeted therapy is being pursued by many companies. The first such biologic to demonstrate clinical benefit in autoimmune disease was ustekinumab, which is now an approved medicine for the treatment of patients with psoriasis and psoriatic arthritis (Stelara® package insert, 2015) and is being evaluated in Phase 3 trials for treatment of CD (Toussirot et al. 2013). Ustekinumab is a monoclonal antibody that recognizes the common p40 subunit of IL-12 and IL-23; therefore, it does not target IL-23 specifically. Blockade of the IL-12 pathway may prevent Th1 cell-induced interferon blockade of Th17 cell development, thus potentially limiting the clinical activity of p40 targeting antibodies. Experimental studies suggest that blocking the

IL-23/Th17/interleukin-17 immune axis (and not IL-12) is sufficient to treat autoimmune inflammation (Monteleone et al. 2009). Interleukin-23-specific medicines targeted to the IL-23 p19 subunit have demonstrated clinical activity in psoriasis and CD (Kopp et al. 2015; Sofen et al. 2014; Krueger et al. 2015; Sands et al. 2015). Although clinical evaluation of an IL-23-targeted therapy in ulcerative colitis has yet to occur, the IL-23/Th17 pathway is suggested to have a significant role in patients with ulcerative colitis (Gheita et al. 2014; Globig et al. 2014; El-Bassat et al. 2014).

LY3074828 is a humanized immunoglobulin G4-variant monoclonal antibody that is directed against the p19 subunit of IL-23 and does not bind IL-12. LY3074828 is being developed for the treatment of autoimmune diseases in which the IL-23 pathway is thought to have a significant pathogenic role. LY3074828 does not bind rodent IL-23, so a surrogate molecule was developed to neutralize mouse IL-23 for use in preclinical studies. Neutralization of IL-23 with this surrogate antibody significantly reduced the development of arthritis and inhibited ileal inflammation in a mouse model of spondyloarthropathy with bowel inflammation (Ruutu et al. 2012). In addition, neutralization of IL-23 significantly reduced the disease score in the relapsing-remitting experimental autoimmune encephalomyelitis (multiple sclerosis-like) model in mice. Anti-IL-23 antibody also demonstrated some efficacy in preclinical arthritis models, depending on the timing of intervention (Cornelissen et al. 2013).

Study I6T-MC-AMAA (AMAA), has been completed to date evaluating LY3074828 in healthy volunteers and in subjects with plaque psoriasis. Seven cohorts of subjects with active psoriasis received single doses of IV LY3074828 (up to 600 mg) or placebo. A single cohort of 5 healthy subjects received single SC doses of LY3074828 (120 mg). A total of 33 subjects with psoriasis and 5 healthy subjects were administered LY3074828. Seven subjects with psoriasis received placebo.

- No serious adverse events (SAEs) were reported. Treatment-emergent adverse events (TEAEs) reported as related to investigational product included one Grade 1 event of diarrhea experienced by a single subject in the 5-mg IV cohort, 2 Grade 1 events of nausea experienced by 2 subjects in the 20-mg IV cohort, one Grade 1 event of headache experienced by a single subject in the 200-mg IV cohort, and five Grade 1 events of injection site pain experienced by 3 subjects in the 120-mg SC cohort. No LY3074828 TEAEs of Grade 2 or higher were reported. No dose-dependent trends in adverse events (AEs) were seen. No clinically important changes in vital signs, electrocardiograms (ECGs), or clinical laboratory results were observed.
- Pharmacokinetic results from Study AMAA indicate that serum exposure of LY3074828 increases in a dose-proportional manner. The mean half-life associated with the terminal rate constant ($t_{1/2}$) was 10.5 days and did not appear to be dependent on dose. The overall mean clearance following IV administration was approximately 0.526 L/day and is within the range expected for human monoclonal antibodies. Maximum concentrations were observed 3 days postdose following SC administration. Based on the area under the concentration versus time curve (AUC), the SC bioavailability was 40%.

- Treatment-emergent anti-drug antibodies (TE-ADAs) developed in 3 subjects after administration of single IV doses of LY3074828, (120 mg, 2 subjects; 350 mg, 1 subject). No subject had TE-ADAs after SC administration. There was no correlation between TE-ADA titers and the doses of LY3074828.

The clinical phase of Study I6T-MC-AMAD (AMAD) has been completed. A total of 43 healthy Japanese and Caucasian subjects were administered LY3074828 or placebo via either IV infusion (60 to 1200 mg) or SC injection (200 mg) in a Phase 1, single-site, subject- and investigator-blind, randomized, placebo-controlled, single-dose study. Subjects were followed-up for up to 12 weeks following the single dose of study drug.

- No SAEs and no AEs considered related to study drug were reported. The reported TEAEs were not dose dependent. There were no infusion reactions or injection site reactions. There were no clinically significant findings in vital signs, ECGs, or clinical laboratory tests, except for 1 subject having an abnormal ECG finding that was mild and not considered to be related to study drug.
- Preliminary PK data available from Study AMAD indicate that the PK of LY3074828 are similar in Japanese and Caucasian subjects.

3.3. Benefit/Risk Assessment

Based on LY3074828 nonclinical and preliminary clinical data, there are no anticipated risks requiring monitoring beyond those of a typical humanized monoclonal antibody in human studies. No clinically significant safety or tolerability concerns have been identified in patients or subjects to date for LY3074828 up to the highest dose given (1200 mg IV, single dose).

More information about the known and expected benefits, risks, SAEs and reasonably anticipated AEs of LY3074828 are to be found in the Investigator's Brochure (IB).

4. Objectives and Endpoints

Table AMAL.1 shows the objectives and endpoints of the study.

Table AMAL.1. Objectives and Endpoints

| Objectives | Endpoints |
|---|--|
| 
Primary
 
To evaluate the relative bioavailability of the LY3074828 lyophilized formulation prepared by reconstitution (Reference) and the extemporaneously prepared formulation (subcutaneous [SC] 2 × 1-mL) when administered to healthy subjects by SC injection.
 | 
Reference versus SC 2 × 1-mL.
 
The ratio of geometric least squares means between the test and reference formulations will be calculated for key pharmacokinetic (PK) parameters of LY3074828.
 
Primary endpoints will be area under the concentration versus time curve (AUC) from time zero to infinity (AUC[0-∞]), and AUC from time zero to time t, where t is the last sample with a measurable concentration (AUC[0-t_{last}]). The secondary endpoints will be maximum observed drug concentration (C_{max}) and time to C_{max} (t_{max}).
 |
| 
Secondary
 
To evaluate the relative bioavailability of LY3074828 extemporaneously prepared as the test formulation when the same volume is administered to healthy subjects by SC injection using a single injection (1 × 2-mL) and 2 injections (2 × 1-mL).
 
To evaluate the absolute bioavailability of LY3074828 extemporaneously prepared as the test formulation when administered to healthy subjects by SC injection compared to intravenous (IV) infusion.
 
To assess the impact of Drug Product formulation changes and number of injections on tolerability of LY3074828.
 | 
SC 2 × 1-mL versus SC 1 × 2-mL of test formulation.
 
The ratio of geometric least squares means between the SC 2 × 1-mL and SC 1 × 2-mL injections will be calculated for key PK parameters of LY3074828.
 
Primary endpoints will be AUC(0-∞) and AUC(0-t_{last}).
 
The secondary endpoints will be C_{max} and t_{max}.
 
SC 2 × 1-mL versus IV; SC 1 × 2-mL versus IV.
 
The ratio of geometric least squares means of the formulations (SC/IV) will be calculated for AUC(0-∞).
 
All treatments.
 
Incidence of treatment-emergent adverse events (TEAEs).
 
Incidence of treatment-emergent anti-drug antibodies (TE-ADAs).
 |

5. Study Design

5.1. Overall Design

Study AMAL is a single-center, randomized, parallel-treatment, open-label, Phase 1 single-dose administration study evaluating LY3074828 in 72 healthy subjects.

Screening Period (≤ 4 weeks): Subjects will be evaluated for study eligibility ≤ 28 days prior to enrollment.

Residential Period (2 days): Subjects who fulfill the eligibility criteria will be randomized to 1 of 4 treatments, with 18 subjects randomized to each treatment, as shown below:

- **Reference:** 250 mg LY3074828; lyophilized reference formulation with $2 \times 1\text{-mL} + 1 \times 1.5\text{-mL}$ SC injections;
- **Test SC $2 \times 1\text{-mL}$:** 250 mg LY3074828; test formulation with $2 \times 1\text{-mL}$ SC injections;
- **Test SC $1 \times 2\text{-mL}$:** 250 mg LY3074828; test formulation with $1 \times 2\text{-mL}$ SC injection;
- **Test IV:** 250 mg LY3074828; test formulation by IV infusion over at least 30 minutes.

Subjects will report to the clinical research unit (CRU) on Day -1 and remain at the CRU until after the scheduled procedures have been completed on Day 2 as defined in the Schedule of Activities (Section 2). After randomization, study drug will be administered by either IV infusion or SC injection in the morning of Day 1 after an overnight fast. Subjects within the same enrollment group may be dosed across several days if required by the site for logistical or other purposes.

Outpatient Follow-up Period (approximately 14 weeks): The follow-up period will include outpatient visits for a total of 12 weeks following Day 1 dose administration to assess tolerability and PK of LY3074828. An end-of-study follow-up visit will be scheduled within 7 to 14 days after the last procedure or upon early discontinuation (ED).

5.2. Number of Participants

A total of 72 subjects will be enrolled to ensure that approximately 64 subjects complete the study (16 completers per treatment). From a data standpoint, a subject's study participation is considered as complete if he/she received the study drug and completes all activities up to and including at least Study Day 29.

5.3. End of Study Definition

End of the study is the date of the last visit or last scheduled procedure shown in the Schedule of Activities (Section 2) for the last subject.

5.4. Scientific Rationale for Study Design

Single doses of 250 mg LY3074828 and the PK sampling timepoints have been selected to generate PK profiles sufficient to fulfill the study objectives.

As the primary endpoints are PK-related and therefore considered to be objective in nature, it is not considered appropriate to include a placebo control during this study. Furthermore, the secondary objective relating to tolerability is a comparison between formulations and therefore addition of a placebo control will not contribute to the scientific validity of the study. As only a single dose level (250 mg) of LY3074828 will be administered during this study, and subjects and site staff will be aware of the administration route (eg, number of SC injections, IV dosing), an unblinded study design has been selected.

Due to the maximum achievable concentration of the lyophilized reference formulation being 72 mg/mL, it is not possible to administer 250 mg with a total injection volume of 2 mL for consistency with the other SC treatments. The total injection volume for the reference formulation was therefore increased to 3.5 mL to ensure a comparable total dose to the test formulation. Although the theoretical total dose for this treatment is 252 mg, the dose levels for all treatments are referred to as 250 mg for the purposes of this protocol.

A parallel-group design was chosen because a crossover design is impractical for compounds that have long half-lives, such as monoclonal antibodies. In addition, a crossover study design could confound PK data if subjects develop neutralizing anti-drug antibodies (ADAs).

5.5. Justification for Dose

CCI

Doses up to 1200 mg were found to be safe when administered by IV infusion in healthy subjects in the single-dose Study AMAD. Subcutaneous bioavailability was approximately 40% in Study AMAA.

The margin of safety for the dose of 250 mg IV relative to the no-observed-adverse-effect level observed in the 6-month nonclinical toxicology study in cynomolgus monkeys is 26.3 based on dose and 7.5 based on AUC ([Table AMAL.2](#)). Margins of safety for the 250 mg SC treatments are expected to be higher than the 250mg IV dose.

Table AMAL.2. Margin of Safety for Intravenous Administration of LY3074828 Based on Administered Dose and Predicted Exposure

| | Dose (mg/kg) | Dose Multiple ^a | AUC _{0-672h,ss} (μ g·h/mL) | Margin of Safety ^b |
|--|--------------|----------------------------|---|-------------------------------|
| Human dose (250 mg IV) ^c | 3.8 (IV) | | 11400 | |
| Monkey NOAEL ^d 6-month study | 100 Q1W (SC) | 26.3 | 85800 ^e | 7.5 |
| Monkey NOAEL ^f 4-week study | 100 Q1W (IV) | 26.3 | 204000 ^g | 17.9 |

Abbreviations: AUC = area under the plasma concentration versus time curve; AUC₀₋₁₆₈ = AUC during the dosing interval;

AUC_{0-672h,ss} = AUC over 672 hours at steady state; IV = intravenous; NOAEL = no observed-adverse-effect level;

SC = subcutaneous; Q1W = once every week.

a Dose multiple is the dose in animals divided by dose in humans.

b Margin of safety is the calculated AUC in animals divided by predicted AUC in humans.

c Highest proposed dose in this study; a body weight of 65 kg is assumed. Phase 2 studies with LY3074828 are primarily using a dosing interval of 4 weeks (672 hours). Human AUC_{0-672h,ss} is equivalent to the expected AUC_{0- ∞} following a single dose in this study. Human AUC_{0-672h,ss} at 250 mg IV is predicted based on the average IV clearance observed in Study I6T-MC-AMAA (0.526 L/day).

d NOAEL was determined in a 6-month repeat dose toxicity study using a Q1W dosing interval (Study 20043324).

e Monkey AUC value was based on average of male and female Day 176 means of AUC₀₋₁₆₈ and has been multiplied by 4 to align with the 4-week AUC interval projected for humans.

f NOAEL was determined in a 1-month repeat-dose toxicity study using a Q1W dosing interval (Study 20029153).

g Monkey AUC value was based on average of male and female Day 29 means of AUC₀₋₁₆₈ and has been multiplied by 4 to align with the 4-week AUC interval projected for humans.

6. Study Population

Eligibility of subjects for study enrollment will be based on the results of screening medical history, physical examination/medical assessment, vital signs, clinical laboratory tests, and ECG.

The nature of any conditions present at the time of the physical examination and any preexisting conditions will be documented.

Screening may occur up to 28 days prior to enrollment. Subjects who are not enrolled within 28 days of screening may be subjected to an additional medical assessment and/or clinical measurements to confirm their eligibility.

Prospective approval of protocol deviations to recruitment and enrollment criteria, also known as protocol waivers or exemptions, are not permitted.

6.1. Inclusion Criteria

Subjects are eligible for inclusion in the study only if they meet all of the following criteria at screening and/or enrollment:

- [1] are overtly healthy males or females, as determined by medical history and physical examination
- [1a] male subjects:
 - agree to not donate sperm for the duration of the study and for 3 months following dosing and to use at least 1 effective method of contraception for the duration of the study or for 3 months following dosing, whichever is longer, as follows:
 - a) Male subjects with non-pregnant partners of childbearing potential must use a male condom with spermicide in addition to another acceptable method of contraception from the following list: female partner with placement of intrauterine device; female partner with established use of oral, injected, or implanted hormonal contraception associated with inhibition of ovulation; male sterilization, with verbal confirmation of surgical success; female partner with bilateral tubal ligation; female partner with established use of progesterone only oral contraception, where inhibition of ovulation is not the primary mode of action; diaphragm, cap, or sponge in conjunction with spermicide
 - b) Male subjects with female partners who are pregnant or breastfeeding should use a condom with spermicide
 - c) For male subjects who are exclusively in same sex relationships, contraceptive requirements do not apply
 - d) For male subjects with female partners of non-childbearing potential, contraceptive requirements do not apply

- e) Male subjects practicing true abstinence, which must be due to the subject's lifestyle choice; ie, the subject should not become abstinent just for the purpose of study participation. Withdrawal or calendar methods are not acceptable.

[1b] female subjects:

- Women of childbearing potential must agree to either remain abstinent or use 2 effective methods of contraception for the entirety of the study. Abstinence or contraception must continue for the duration of the study or for 3 months following the dose of investigational product, whichever is longer.
- a) Women of child-bearing potential must test negative for pregnancy prior to initiation of treatment as indicated by a negative pregnancy test at the screening visit followed by a negative pregnancy on Day -1.
- b) Women of childbearing potential must use a male condom with spermicide in addition to another acceptable method of contraception from the following list: placement of intrauterine device; established use of oral, injected or implanted hormonal contraception associated with inhibition of ovulation; partner with male sterilization, with verbal confirmation of surgical success; bilateral tubal ligation.

Women not of childbearing potential may participate, and include those who are:

- a) Infertile due to surgical sterilization (at least 6 weeks after hysterectomy, bilateral salpingectomy, bilateral oophorectomy), congenital anomaly such as mullerian agenesis; or
- b) Postmenopausal – defined as a woman at least 50 years of age with an intact uterus, not on hormone therapy, who has had at least 6 months of spontaneous amenorrhea with a follicle-stimulating hormone >40 mIU/mL

- [2] are between 18 and 65 years of age, inclusive, at the time of screening
- [3] have a body mass index (BMI) of 18.0 to 32.0 kg/m², inclusive, at screening
- [4] have clinical laboratory test results within normal reference range for the investigative site, or results with acceptable deviations that are judged to be not clinically significant by the investigator
- [5] have venous access sufficient to allow for blood sampling and administration of investigational product for IV administration as per the protocol
- [6] are reliable and willing to make themselves available for the duration of the study and are willing to follow study procedures
- [7] are able and willing to give signed informed consent

6.2. Exclusion Criteria

Subjects will be excluded from study enrollment if they meet any of the following criteria at screening and/or enrollment:

- [8] are investigative site personnel directly affiliated with this study and their immediate families. Immediate family is defined as a spouse, biological or legal guardian, child, or sibling.
- [9] are Lilly or Covance employees
- [10] are currently enrolled in a clinical trial involving an investigational product or any other type of medical research judged not to be scientifically or medically compatible with this study
- [11] have participated, within the last 3 months prior to screening, in a clinical trial involving an investigational product. If the previous investigational product has a long half-life, 3 months or 5 half-lives (whichever is longer) should have passed
- [12] have previously completed or withdrawn from this study or any other study investigating LY3074828, and have previously received the investigational product
- [13] have known allergies to LY3074828, related compounds or any components of the formulation, or history of significant atopy
- [14] have an abnormality in the 12-lead ECG that, in the opinion of the investigator, increases the risks associated with participating in the study
- [15] have an abnormal blood pressure as determined by the investigator
- [16] have a history or presence of cardiovascular, respiratory, hepatic, renal, gastrointestinal, endocrine, hematological (including thalassemia and serious glucose-6-phosphate dehydrogenase deficiency), or neurological disorders capable of significantly altering the absorption, metabolism, or elimination of drugs; of constituting a risk when taking the investigational product; or of interfering with the interpretation of data
- [17] have known or ongoing psychiatric disorders deemed as clinically significant by the investigator
- [18] regularly use known drugs of abuse and/or show positive findings on urinary drug screening
- [19] show evidence of human immunodeficiency virus (HIV) infection and/or positive human HIV antibodies
- [20] show evidence of hepatitis C and/or positive hepatitis C antibody
- [21] show evidence of hepatitis B and/or positive hepatitis B surface antigen and/or hepatitis B core antibody (HBcAb+)
- [22] are women who are lactating

- [23] have used or intend to use over-the-counter or prescription medication, including herbal medications such as St. John's Wort within 14 days prior to dosing (stable doses of oral contraceptive or hormone replacement therapy may be allowed as per judgment of the investigator)
- [24] have donated blood of more than 500 mL within the last month prior to screening
- [25] have an average weekly alcohol intake that exceeds 28 units per week (males) and 21 units per week (females), (1 unit alcohol equals 1/2 pint [285 mL] of beer, 1 glass [125 mL] of wine, or 25 mL of distilled spirits) and/or show positive findings on ethanol testing and/or who are unwilling to abide by the alcohol restrictions described in Section [6.3.2](#)
- [26] are subjects whose tobacco consumption is more than 10 cigarettes per day or the equivalent or subjects who are not willing to refrain from smoking for approximately 1 hour prior to each ECG and vital sign measurement during the study or who are unwilling to abide by the CRU smoking guidelines described in Section [6.3.2](#)
- [27] have had symptomatic herpes zoster within 3 months of screening
- [28] show evidence of active or latent tuberculosis (TB), as documented by medical history and examination and TB testing: a negative (not indeterminate) QuantiFERON®-TB Gold test, or have had household contact with a person with active TB, unless appropriate and documented prophylaxis for TB has been given.
- [29] have received live vaccine(s) (including attenuated live vaccines, and those administered intranasally) within 1 month of screening, or intend to during the study
- [30] are immunocompromised
- [31] have received treatment with biologic agents (such as monoclonal antibodies, including marketed drugs) within 3 months or 5 half-lives (whichever is longer) prior to dosing.
- [32] have significant allergies to humanized monoclonal antibodies
- [33] have clinically significant multiple or severe drug allergies, or intolerance to topical corticosteroids, or severe post treatment hypersensitivity reactions (including, but not limited to, erythema multiforme major, linear immunoglobulin A dermatosis, toxic epidermal necrolysis, or exfoliative dermatitis)
- [34] have had lymphoma, leukemia, or any malignancy within the past 5 years except for basal cell or squamous epithelial carcinomas of the skin that have been resected with no evidence of metastatic disease for 3 years
- [35] have had breast cancer within the past 10 years

- [36] in the opinion of the investigator or sponsor, are unsuitable for inclusion in the study

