9.4.3. Electrocardiograms

For each subject, ECGs should be collected according to the Schedule of Activities (Section 2) and following the study-specific recommendations included in the Manual of Operations for the study.

Any clinically significant findings from ECGs that result in a diagnosis and that occur after the subject receives the first dose of the investigational product, should be reported to Lilly, or its designee, as an AE via eCRF.

For each subject, a single 12-lead digital ECG will be collected according to the Schedule of Activities (Section 2). Electrocardiograms must be recorded before collecting any blood for safety or PK tests. Subjects must be supine for at least 5 minutes before ECG collection and remain supine but awake during ECG collection. Electrocardiograms may be obtained at additional times, when deemed clinically necessary by the investigator. All ECGs recorded should be stored at the investigational site.

Electrocardiograms will be interpreted by a qualified physician (the investigator or qualified designee) at the site as soon after the time of ECG collection as possible, and ideally while the subject is still present, to determine whether the subject meets entry criteria at the relevant visit(s) and for immediate subject management, should any clinically relevant findings be identified.

If a clinically significant finding is identified (including, but not limited to, changes in QT/corrected QT [QTc] interval from baseline) after enrollment, the investigator will determine if the subject can continue in the study. The investigator, or qualified designee, is responsible for

determining if any change in subject management is needed, and must document his/her review of the ECG printed at the time of collection. Any new clinically relevant finding should be reported as an AE.

9.4.4. *Tuberculosis Testing*

Subjects will be tested as indicated in the Schedule of Activities (Section 2) for evidence of active or latent TB using the QuantiFERON-TB Gold test. If the test is indeterminate, 1 retest is allowed. If the retest is indeterminate, then the subject is excluded from the study.

Subjects who have had household contact with a person with active TB must be excluded unless appropriate and documented prophylaxis for TB has been given.

Subjects with any history of **active** TB are excluded from the study, regardless of previous or current TB treatments.

9.4.5. *Safety Monitoring*

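### Exclusion [28] names a negative QuantiFERON result where the excluding result belongs, and its prophylaxis exception leaves treated latent TB unsettled

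*Protocol*

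**What the plan says.** The lead-in to Protocol section 6.2 reads: "Subjects will be excluded from study enrollment if they meet any of the following criteria at screening and/or enrollment". Every item below it must therefore describe a reason to keep a subject out.

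Item [28] opens with evidence of active or latent TB, "as documented by medical history and examination and TB testing: a negative (not indeterminate) QuantiFERON®-TB Gold test". It then adds a second ground and closes with an exception: "or have had household contact with a person with active TB, unless appropriate and documented prophylaxis for TB has been given".

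Section 9.4.4 (Tuberculosis Testing) sets the rest of the rule in four statements:

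- Subjects are tested "for evidence of active or latent TB using the QuantiFERON-TB Gold test".
- On unclear results: "If the test is indeterminate, 1 retest is allowed. If the retest is indeterminate, then the subject is excluded from the study".
- On contact: "Subjects who have had household contact with a person with active TB must be excluded unless appropriate and documented prophylaxis for TB has been given".
- Any past active TB excludes, whatever treatment was or is being given.

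The Schedule of Activities and Appendix 2 place the QuantiFERON test at screening only. It is the only TB laboratory test in the plan.

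**The concern.** Read word for word, [28] offers a negative test as the documentation of TB. That phrase would fit an inclusion criterion and has the wrong sense in an exclusion list. A site looking for the plain statement that a positive test excludes will not find it in either place.

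The second difficulty is how far the closing exception reaches. It comes after both grounds and is set off by a comma, so it can be taken to cover TB evidence as well as household contact. A subject with a positive test and documented preventive treatment might then be admitted at one reading and refused at another.

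This is a safety criterion for healthy volunteers given an antibody against IL-23. Section 3.2 of the Protocol notes that cells responding to IL-23 matter for resistance to infection. The wording is also applied strictly: section 6 permits no waivers, section 6.4 does not allow screen failures to be rescreened, and section 8.1.1 discontinues anyone enrolled by mistake. A misreading could therefore cost a subject's place or lead to a discontinuation after dosing.

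**Working it through.** No formula applies and the plan states no figure to reproduce. The check sets the texts side by side.

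**Step 1: which result is named.** Two places set the TB eligibility rule, [28] and 9.4.4. The number that say in words that a positive result excludes is 0 of 2. The number that name a negative result in the excluding position is 1 of 2, namely [28].

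**Step 2: comparison with the neighboring items.** The other infection-test exclusions are [19] (HIV), [20] (hepatitis C) and [21] (hepatitis B). All 3 of 3 name the positive result; [20], for instance, reads "show evidence of hepatitis C and/or positive hepatitis C antibody". Item [28] departs from the protocol's own pattern. The sentence is complete, so neither redaction nor text extraction explains it.

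**Step 3: scope of the exception.** In [28] the prophylaxis clause follows 2 grounds. In 9.4.4 it is tied to 1, household contact.

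**Step 4: each case under both texts.**

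| Case | Item [28] | Section 9.4.4 | Read together |
|---|---|---|---|
| Negative test, no other ground | Named in the excluding position | Not mentioned | Eligible, by inference |
| Positive test, no prophylaxis | Result not named; falls under TB evidence | Test is for that evidence; exclusion not stated | Excluded, by inference |
| Indeterminate, then indeterminate on retest | Not named as excluding | Excluded | Excluded, stated |
| Household contact, no prophylaxis | Excluded | Excluded | Excluded, stated |
| Household contact, documented prophylaxis | Exception applies | Exception applies | Not excluded on this ground |
| Past active TB, treated | Wide reading could admit | Excluded whatever the treatment | Excluded, stated |
| Latent TB, treated | Wide reading admits; narrow reading excludes | No exception given, none expressly refused | Open |

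Two rows rest on inference and one is unresolved. The schedule and the laboratory list are left out of the counts, because a rule on results would not be expected there.

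**The case against.** The strongest reply is that no site would act on the literal words. The operative phrase in [28] is evidence of active or latent TB, and 9.4.4 names QuantiFERON as the test for it, so a positive result excludes once the two are combined. The result whose handling is least obvious, an indeterminate one, is fully specified. Other safeguards exist: inclusion [4] asks for laboratory results that are normal or not clinically significant in the investigator's judgment, Appendix 2 lists QuantiFERON among the laboratory tests, and [36] excludes those who "in the opinion of the investigator or sponsor, are unsuitable for inclusion in the study". All of this stands, and it is why the impact is low. It does not make the wording of [28] right.

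On the exception, the clause directly follows household contact, so the natural reading limits it to that ground, and 9.4.4 repeats it for that ground alone. This also stands for the most part. What it does not settle is treated latent TB, since 9.4.4 neither grants nor expressly refuses an exception there.

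A reader might go further and infer that the protocol leaves sites without a TB rule, or that it would admit subjects with active TB who had received prophylaxis. The documents support neither. The rule can be recovered from the two sections, and 9.4.4 shuts out any history of active TB regardless of treatment. The two sections conflict only if the wide reading of [28] is chosen, and a consistent narrow reading is available.

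**Conclusion.** Item [28] is wrong as written, with low impact. That it names the entry-qualifying result in an exclusion, and that no sentence says a positive result excludes, is plain from the text. That the exception reaches too far is a possible reading only. After the active-TB-history sentence in 9.4.4 is taken into account, the one open case is latent TB that has been treated.

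The counts in the check describe wording and do not measure an effect on subjects. Any estimate of subjects affected would need a TB prevalence in the recruited population, which the documents do not give. That the number is small is an expectation, resting on healthy volunteers, recoverable intent and the other eligibility safeguards. Nothing here bears on the sample size, the endpoints or the PK analysis.

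**What to change.** Reword [28] so that it excludes a subject who meets any one of these:

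- any history of active TB, treated or not;
- evidence of active or latent TB from medical history, from examination, or from testing, where testing means a positive QuantiFERON-TB Gold result or an indeterminate result on the one permitted retest;
- household contact with a person who has active TB, unless suitable prophylaxis is documented, with that exception stated to apply to household contact only.

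The three sources of evidence should be joined by or, so that the item cannot be read as requiring all of them. Add one sentence to 9.4.4 that a positive result excludes. If the sponsor intends to admit treated latent TB, it should say so explicitly in both [28] and 9.4.4 instead; only the sponsor can decide that.

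The cost is a protocol wording amendment with its ethics committee step, and possibly a few more screen failures if sites would otherwise have admitted treated latent TB. No test, visit or subject is added.
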